## 12.0 Participant Information

### 12.1 Subject Population:

Active-duty, male, SFG (18-series) personnel, between the ages of 18-45 (inclusive) years old

### 12.2 Age Range:

Check all the boxes that apply. if the age range of potential subjects (specimens, records) does not match the range(s) selected, please specify in the text box.

- 0-17
- 18-24
- 25-34
- 35-44
- 45-54
- 55-64
- 65-74
- 75+

18-45 (inclusive)

### 12.3 Gender:

- Male
- Female
- Other

### 12.4 Special categories, check all that apply

- Minors /Children
- Students
- Employees - Civilian
- Employees - Contractor
- Resident/trainee
- Cadets /Midshipmen
- Active Duty Military Personnel
- Wounded Warriors
- Economically Disadvantaged Persons
- Educationally Disadvantaged Persons
- Physically Challenged (Physical challenges include visual and/or auditory impairment)
- Persons with Impaired Decisional Capacity
- Prisoners
- Pregnant Women, Fetuses, and Neonates
- Non-English Speakers
- International Research involving Foreign Nationals - Headquarters Review is necessary

You must also consider the requirements of DoDI 3216.02, Enclosure 3, paragraph 7.e.

### 12.5 Inclusion Criteria:

Order Number	Criteria
1	Active-Duty Special Forces Personnel (18-series)
2	Between the ages of 18-45 years old (inclusive)
3	Male
4	Able to read and understand English language for consent purposes
5	Able to commit to study intervention and follow-up
6	Able to participate in THOR3 coach-lead training, without restriction

## 12.6 Exclusion Criteria:

Order Number	Criteria
1	Obese (body fat $\geq$ 25%)
2	Cardiovascular disease
3	Use of select medications: 

• statins (e.g., Atorvastatin/Lipitor, Fluvastatin, Lovastatin, Pitastatin, Pravastatin, Rosuvastatin/Crestor, Simvastatin/Zocor),

• diuretics (e.g., Microzide, Lasix, Aldactone, Midamor), or

• antihypertensive agents

4	Female
5	Tattoo in treatment area
6	Diagnosis with porphyria (light induced allergy) or photosensitive eczema
7	Current use of medications associated with sensitivity to heat or light (e.g., amiodarone, chlorpromazine, doxycycline, hydrochlorothiazide, nalidixic acid, naproxen, piroxicam, tetracycline, thioridazine, voriconazole),
8	Use of pacemaker/underlying cardiac disease
9	Diagnosis of autoimmune diseases
10	Albinism
11	Peripheral neuropathy

## 13.0 Recruitment and Consent

### 13.1 Please describe the recruitment process, including how subjects will be identified and selected for the study.

Study activities will occur at Joint Base Lewis-McChord (JBLM) within the 1st Special Forces Group (SFG). Study activities, including recruitment, will occur in the THOR3 area or other applicable 1st SFG areas.

**Recruitment, Pre-Screening (before consent), Study Introduction & Informed Consent:**  
Potential participants will be identified via three methods:

1. Participants may self-refer to participate in the study if they become aware of the study by study flyer (Appendix P) or word of mouth. Interested potential participants will be able to contact a member of the study team via phone or email.
2. Mass briefs at THOR3 coach-lead trainings.
  - Briefings will occur at regular intervals, about every 3 weeks, for each training class at the 3 Operator focused training sessions. In the course of a month, there will be about 4 briefings.
  - Briefings will take no more than five (5) minutes. The briefs will be scheduled to occur prior to the coach lead session. Consenting procedures will not occur during these informational briefs.

- Leadership would only include the OIC of THOR3, not Group Leadership. Every effort will be made to ensure there is not undue coercion.
- "Thank you for taking a few minutes to listen to this brief. We are conducting a research study to assess utilizing light therapy to increase recovery post training. There is the possibility that it can decrease inflammation, soreness, and fatigue and thus increase performance. We will ask you to complete a baseline visit, where we collect some self-reported demographic and health information, and measure your height, weight, and body fat. We will also ask you to complete a strength test and a counter movement jump. We will assign you an Oura Ring to wear for the duration of the study. This visit will take about 45 minutes. Then for 3 weeks, we will ask to provide light therapy 3 times a week after THOR3 coach led training. You will be randomly assigned to an active treatment or sham treatment group. Each group will wear headphones and blackout glasses. These sessions should take 20 minutes. Each week we will ask you to complete a countermovement jump, and fill out some questionnaires. These visits will take about 15 minutes. We will also ask you to fill out a daily pain questionnaire, and complete an activity log, which will take about 5 minutes. At the end of the three weeks, we will test your strength and counter movement jump again and ask you to fill out final questionnaires. This will take about 25 minutes. You will be compensated at each weekly visit, for a total of 150 USD."

3. Study advertisements (Appendix P) will be posted in THOR3 and 1st SFG areas that operators frequent.

If a potential participant expresses interest in learning more about the research study, a member of the research staff will briefly introduce the study, express the voluntary nature of participation, assess interest in participating, and screen the potential participant for eligibility. Eligibility will be determined in person (individually, with a study team member) using the Inclusion/Exclusion Case Report Form (CRF) (Appendix A). Additionally, the potential participant may be provided with a study flyer.

Pre-screening conversations may also take place over the phone, should a participant contact the study team, using the Screening Script (Appendix M). Potential participants who meet initial eligibility per the Screening Script and express interest in participating will be asked to come to the THOR3 area to confirm final eligibility with an authorized study team member.

If the potential participant meets eligibility criteria and expresses interest in participating, an authorized study team member will assess whether the individual is comfortable with a group consent or an individual consent discussion. In accordance with the individual's preference, the authorized study team member will initiate the formal consent discussion and, if applicable, obtain informed consent (as outlined in Protocol Section 13.4).

If a potential participant would like additional time to review the consent form, study procedures, risks and benefits, etc. they will be provided with a consent form to take home and, if applicable, they may return at a later date to have any and all remaining questions answered and to finish the consent process.

The research team will keep a password-protected electronic Screening Log (Appendix N), containing initials, date of birth (DOB) and eligibility/ineligibility status, in a secure folder on a secure drive, accessible only by authorized users. This log is needed to avoid any duplicative screening of individuals. This log, therefore, will include initials and dates of birth (DOBs) for those that screened formally and informally. Screening IDs will be different from study IDs that are assigned post-consent.

## 13.2 Compensation for Participation:

Participants may receive up to \$150 for participation in this research.

Participants will be compensated at the following intervals:

- \$50 USD gift card for completing the activity log and turning it in at the 1-week follow-up
- \$50 USD gift card for completing the activity log and turning it in at the 2-week follow-up
- \$50 USD gift card for completing the activity log and turning it in at the 3-week follow-up

Eligible participants will be compensated through the Greenphire platform. Participants will be registered in the Greenphire platform upon confirmation of final eligibility. Once registered, the participant will be classified as a (1) non-active duty, or (2) active-duty employee category, and a Greenphire debit card will be assigned to them. Participants will be given an envelope containing their debit card and all information needed to access their funds, and they will be

instructed to retain that card for the duration of their study participation. At the various compensation intervals indicated above, an assigned user will verify the study visit was completed and will issue a stipend through the Greenphire system, which will electronically release funds to the assigned debit card.

If needed, a Greenphire debit card can be mailed to a participant. In this case, a participant will be registered into the appropriate employee category, the debit card will be assigned (but not activated) and will be mailed to the participant. Stipends will be issued only after the participant confirms receipt of the card.

DHA-AI 3200.01 indicates active-duty service members may receive additional compensation for the completion of a daily health diary when completed off-duty. In accordance with DHA-AI 3200.01 the following definitions of on-duty and off-duty will apply to active duty-service member study participants:

- An individual is on-duty when they are expected or required to perform the duties of their assigned job or position.
- An individual is off-duty if the individual is not scheduled to perform any work that may arise during the period.

### **13.3 Please describe the pre-screening process. If no pre-screening, enter Not Applicable in the text editor**

If a potential participant expresses interest in learning more about the research study, a member of the research staff will briefly introduce the study, express the voluntary nature of participation, assess interest in participating, and screen the potential participant for initial eligibility using the Inclusion/Exclusion CRF (Appendix A). Pre-screening conversations may take place over the phone using the Screening Script (Appendix M).

### **13.4 Consent Process: Revised Common Rule, Section 219.116: General requirements for informed consent, whether written or oral, are set forth in this paragraph and apply to consent obtained in accordance with the requirements set forth in paragraphs (b) through (d) of this section. Broad consent may be obtained in lieu of informed consent obtained in accordance with paragraphs (b) and (c) of this section only with respect to the storage, maintenance, and secondary research uses of identifiable private information and identifiable biospecimens.**

Are you requesting a waiver or alteration of informed consent?

Yes  No

Please explain the consent process:

Consent (individual and group) will be obtained in accordance with principles of Belmont Report and Common Rule guidelines.

The potential participant(s) will be given a copy of the ICF to read before the informed consent discussion with an authorized study team member. Sufficient time will be given to the potential participant to understand the study purpose, study procedures, time commitments, potential risks and benefits, and the types of information that will be collected and used by the research team if they agree to participate in the study.

Questions can be raised by the potential participant(s) at any time. The potential participant(s) will be reminded that their participation is completely voluntary and that they may withdraw from the study at any time without penalty. Their decision to participate, or not, will not affect their access to health care that they are otherwise entitled to and it will not affect their military position.

Formal consent, as represented by the act of signing a dated, IRB-approved ICF for the study will occur after: confirming eligibility using the Inclusion/Exclusion CRF, a thorough review of what is involved in the study (including all available study treatments as well as blinding and randomization processes), and all questions have been answered. Informed consent will be obtained in person and may include consenting as a group, based on the participants' comfortability and scheduling. Each individual will be asked for their preference for a group or individual consent discussion, and the individual's preference will be utilized. A copy of the signed consent form will be given to the participant and the original will be securely stored. No Legally Authorized Representatives will be utilized.

Every effort will be made to eliminate the perception of authority. When applicable, the study investigators will be in civilian clothes instead of uniform and will not utilize or display their military rank when introducing themselves. Some potential participants may be patients of the study PI or AI. In these cases, the consent conversation will be initiated by non-provider study staff to prevent any misconception of coercion or undue influence.

In the event that there are significant new findings that may affect participants' willingness to continue in the study, an information sheet will be provided to all current and past participants, and the ICF will be amended for future participants.

Following completion of informed consent, a unique study ID will be generated. This coded study ID will be used on all research data collection forms in place of the participant's name, Department of Defense (DoD) ID, or other protected identifier. No PII will be entered into REDCap.

**13.5 DoDI 3216.02 requires an ombudsman to be present during recruitment briefings when research involves greater than minimal risk and recruitment of Service members occurs in a group setting. If applicable, you may nominate an individual to serve as the ombudsman.**

- N/A
- Propose ombudsman

**13.6 Withdrawal from Study Participation:**

Explain the process for withdrawal and specify whether or not the subjects will be given the opportunity to withdraw their data their data/specimens in the event they wish to withdraw from the study

**Participant Withdrawal:**

Participants may contact a member of the study team in writing to formally withdraw from the study.

Participants may withdraw from the study at any time without penalty. Participants will be informed that withdrawal will not affect their access to health care that they are otherwise entitled to and it will not affect their military position.

If a participant withdraws from the study, we may retain and analyze all coded/de-identified data collected up to the time of withdrawal if the data is necessary to maintain the integrity of the study. However, no further data will be collected after the date of withdrawal.

**Withdrawal Without Participant Consent:**

A participant may be withdrawn from the study without their consent if remaining in the study might be dangerous or harmful to them, the military mission requires it, they lose their right to receive medical care at a military hospital, the study is canceled, they fail to adhere to the protocol and/or therapy plan, or if they display inappropriate behavior towards study personnel.

Participants will be asked to return all study materials at the time of study withdrawal. Participants will be contacted up to three times for each contact method (e.g., call, text, email, or in-person interactions) to retrieve the study materials. Once all attempts are exhausted, no further contacts will be made.

**14.0 Risks and Benefits**

**14.1 Risks of Harm:**

Identify all research-related risks of harm to which the subject will be exposed for each research procedure or intervention as a result of participation in this study. Consider the risks of breach

of confidentiality, psychological, legal, social, and economic risks as well as physical risks. Do not describe risks from standard care procedures; only describe risks from procedures done for research purposes

The risks associated with PBMT are minimal. PBMT is used by a variety of healthcare practitioners for painful clinical conditions. Mild discomfort may be experienced during the treatment, the treatment should not feel "hot", but participants should notify the study team member if they feel any uncomfortable warming. Individuals with neuropathies or difficulty distinguishing changes in skin temperature are at higher risk. Potential research-related risks include damage to eye structures, headaches post-procedure, uncomfortable skin heating or erythema/redness, which are both very rare.

The risks associated with the counter-movement jump and strength testing are minimal risks that may be experienced in everyday life, including loss of balance, fall, discomfort, or injury.

Additionally, any time information is collected for a study, there is a small risk of breach of confidentiality.

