#### Photobiomodulation Treatment (PBMT)

PBMT will be delivered at 40W. A member of the study team will use the quadriceps measurements of the treatment area to calculate the PBMT treatment time (approximately 5-20 minutes). PBMT treatment will be provided up to 3 times a week, for 3 weeks. Participants will be asked to engage in 3 sessions per week; however, due to operational demands, we understand that they may not be able to attend all sessions and will then aim to minimally have them attend 2 sessions per week.

PBMT will be provided by a trained study team member. Training for the PBMT will be conducted by a LightForce representative. PBMT will be delivered using the LightForce® XLi 40W device with the Smart Hand Piece technology, created by LiteCure, LLC/DJO (New Castle, DE) which has a built-in accelerometer in the hand piece that controls the speed of light delivery to the treatment area. The LightForce® XLi therapy laser is an FDA cleared device for the treatment of pain. The trained team members will use the Smart Hand Piece technology, which achieves effective treatments and improves dosing accuracy by assessing the operator's speed and providing real-time visual (red – amber – green light) and sensory feedback. The Smart Hand Piece is calibrated to shut-off when moving too slowly, and warn the operator when moving too fast by vibrating. (See LightForce Brochure). The therapy is delivered through a flexible optical fiber threaded through the hand piece, which contains a rolling glass massage ball. PBMT will be delivered at specified J/cm^2 and applied to the quadriceps area.

In order to facilitate participant blinding to their randomized study group, all participants (regardless of their assigned study group) will be asked to wear blackout glasses and headphones during their treatment.

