#### **14.2**

#### **Measures to Minimize Risks of Harm (Precautions, safeguards):**

For each research procedure or intervention, describe all measures to minimize and/or eliminate risk of harms to subjects and study personnel

All available measures to minimize risks will be taken in accordance with standard clinic protocols.

Protective eyewear will be worn by all participants and study team members during PBMT and sham PBMT treatment sessions to avoid potential eye damage. Along with the Laser Safety Officer (LSO), the PI will ensure that the treatment space meets all regulatory requirements for utilization of a treatment laser, including appropriate signage and use of laser blocking screens to absorb any potential scatter/refraction of light outside of the treatment area.

In the rare occurrence that participants experience uncomfortable warmth over the treatment area during PBMT, the treatment will be modified or stopped.

All available measures will be taken by research staff to protect participant confidentiality. See Protocol Section 14.3 for additional information on confidentiality protections.

All participants will be evaluated for AEs at each follow-up visit. All AEs, regardless of severity, will be reported to the PI and the IRB according to the guidelines stated in Protocol Section 16.0.

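### Section 14.1 names two traits that raise the risk from laser warming, but the eligibility criteria address only one of them

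*Combined protocol and SAP*

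**What the plan says.** Section 14.1 calls the risks of PBMT minimal and uncomfortable skin heating very rare. It says that "participants should notify the study team member if they feel any uncomfortable warming" and then adds: "Individuals with neuropathies or difficulty distinguishing changes in skin temperature are at higher risk".

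Section 14.2 gives the action to take: "In the rare occurrence that participants experience uncomfortable warmth over the treatment area during PBMT, the treatment will be modified or stopped".

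Section 12.6 lists 11 exclusions. Item 11 is "Peripheral neuropathy". Item 7 begins "Current use of medications associated with sensitivity to heat or light". Section 12.5 lists 6 inclusion criteria; the one nearest to physical fitness is "Able to participate in THOR3 coach-lead training, without restriction".

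Section 10.1 (Photobiomodulation Treatment) sets delivery at 40W, up to 3 times a week for 3 weeks, by a trained team member. The hand piece gives the operator colour feedback on speed, vibrates if moved too fast, and shuts off if moved too slowly. All participants "will be asked to wear blackout glasses and headphones during their treatment".

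**The concern.** The protocol identifies a trait that raises risk, and the trait is the inability to sense what the participant is asked to report. Both the request to speak up in section 14.1 and the modify-or-stop rule in section 14.2 start from the participant noticing warmth. A man who has trouble judging skin temperature is the one least likely to set either in motion, and nothing in the listed criteria keeps him out or flags him before the first session.

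At stake is an avoidable skin-heating event in a participant of a kind that the protocol had already marked as higher risk. Only the active arm is exposed, because the sham device stays in standby. Treatment effect estimates, power and interpretation are not affected.

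**Working it through.** No arithmetic settles this point, and the plan gives no figure to reproduce. The check sets the sections side by side.

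1. **Risk descriptors (section 14.1).** There are two, joined by *or*: neuropathies, and trouble telling changes in skin temperature.

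2. **Match for the first.** Exclusion 11 covers it, though only in part: it is limited to the peripheral form, while section 14.1 speaks of neuropathies in general.

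3. **Match for the second.** None of the 11 exclusions mentions it. Item 7 is the nearest in wording, but it concerns medications linked to sensitivity to heat or light, which is not a reduced ability to feel heat. None of the 6 inclusion criteria mentions it either. Inclusion 6 concerns ability to train and says nothing about sensation in the skin.

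4. **Count.** Of 2 descriptors, 1 has a matching exclusion, and that match is partial. For the other, the count is 0 of 11 exclusions and 0 of 6 inclusions.

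5. **Safeguards that need the participant's sensation.** These are the request to report warming (14.1) and the rule to modify or stop (14.2).

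6. **Safeguards that do not need it.** The hand-piece shut-off (10.1) limits slow movement, although nothing in that section says that it measures skin temperature. The operator is a trained person delivering treatment by hand. Section 9.4 calls the trial single-blind and section 10.1 blinds the participant, so nothing in the plan stops the operator from watching the skin.

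7. **What could reveal the trait before treatment.** The baseline form (section 10.2, Appendix D) collects self-reported medical history. No check of temperature sensation is listed among the baseline measures in section 10.1 or 10.2. The adverse event review in section 14.2 takes place at follow-up visits, after exposure has begun.

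8. **Exposure.** For a man in the active arm: 3 sessions a week × 3 weeks = up to 9 sessions.

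The forms that would carry a screening question, Appendices A and M, are not among the documents. Section 10.2 describes Appendix A as verifying the eligibility criteria, and the listed criteria contain no such item. A question on one of those forms still cannot be ruled out.

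**The case against.** The strongest reply is that section 14.1 is a risk disclosure. Saying that a trait raises risk does not promise to exclude everyone who has it, and no section says that all higher-risk men are excluded. That is correct. A reader might infer that the protocol contradicts itself, and the documents do not support this reading. What they show is a named risk group with no stated handling before treatment.

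The second reply is that the two descriptors overlap. Peripheral neuropathy is one cause of poor temperature sensation, so exclusion 11 already removes part of the second group. The rest is likely to be small among active-duty men aged 18 to 45 who train without restriction. This limits the size of the gap but does not close it: a man with a known deficit and no neuropathy diagnosis meets no listed exclusion.

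The third reply is that other protections exist: the speed shut-off, the operator, the medical history and the power in section 13.6 to withdraw a participant for whom staying in might be dangerous. These count. A reader might infer that protection rests on the participant's sensation alone, and section 10.1 shows that it does not. However, none of these is a screen for the trait, and withdrawal on safety grounds helps only if someone knows of the problem.

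A reader might also infer that the headphones prevent staff from questioning the participant. The plan does not say that they block speech, and nothing stops him from speaking up. Section 14.2 requires protective eyewear in any case, so restricted sight is not solely a product of blinding.

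**Conclusion.** The concern holds in a limited form. Section 14.1 names two higher-risk descriptors and the eligibility criteria take up one. For the other, the participant-triggered heat safeguards are at their weakest, and what remains is partial protection from the hand piece and the operator.

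The number of men affected cannot be estimated. The documents give no frequency of impaired temperature sensation, and any percentage applied to the 116 requested would be a guess. It is probably small, given the population, the overlap between the descriptors and the protocol's own description of heating as very rare. The conclusion rests on the text of sections 12.5, 12.6, 14.1 and 14.2, and on the assumption that Appendices A and M follow the listed criteria. If either form already asks the question, what remains is to bring section 12.6 into line with it.

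The change is worth making because it bears on safety and costs little. It does not threaten the trial.

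**What to change.** Reconcile sections 12.6, 14.1 and 14.2 so that both higher-risk descriptors are handled before treatment. There are two ways to do this, and the choice belongs to the investigators and the IRB:

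- carry the second descriptor, in the words of section 14.1, into the eligibility criteria and, if not already there, into Appendices A and M as a self-report item; or
- state that men in this group may enrol, and name the safeguard that applies to them and does not depend on their own sensation.

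In the same edit, make clear whether exclusion 11 is meant to be narrower than the neuropathies named in section 14.1.

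The first route costs one clause and one screening question, with no added procedure, and possibly a few fewer eligible men. Its limit should be acknowledged: self-report finds only men who are aware of a deficit. The second route costs a short statement in sections 14.1 and 14.2 and loses no eligible men.
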